1 SYNOPSIS

| | | |
|--|---|--|
| Name of Sponsor/Company: GE Healthcare Ltd. and its Affiliates | Individual Study Table Referring to Part of Dossier in Which the Individual Study or Study Table is Presented: | (For National Authority Use Only) |
| Name of Finished Product: DaTSCAN™ | Volume: | |
| Name of Active Ingredient: Ioflupane (¹²³ I) | Reference: | |
| Title of Study: A phase 1, nonrandomised, noncomparative, open-label study to assess the safety, biodistribution, and internal radiation dosimetry of a single dose of DaTSCAN™ ioflupane (¹²³ I) injection in Chinese healthy volunteers. | | |
| Protocol Number: GE-001-023 | | |
| Investigators and Study Centre: This study will be conducted in a single study centre in the People's Republic of China | | |
| Phase of Development: Phase 1 | | |
| Objectives: Primary Objective: 
To evaluate the safety of a single dose of ioflupane (¹²³I) injection in Chinese healthy volunteers (HVs) Secondary Objectives: 
To determine the biodistribution, internal radiation dosimetry, and effective dose (ED) of ioflupane (¹²³I) injection after intravenous (IV) administration in Chinese HVs.To compare biodistribution and dosimetry findings in this Chinese group with those previously established in European HVs.To compare brain single photon emission computed tomography (SPECT) imaging results in this Chinese group with those previously established in European HVs. | | |
| Study Design: This is a phase 1, single-centre, single-group, nonrandomised, noncomparative, open-label, single-dose study to evaluate the safety, biodistribution, internal radiation dosimetry, and ED of DaTSCAN™ ioflupane (¹²³ I) injection in Chinese HVs. Eight evaluable subjects (4 males and 4 females) will be included in the study. The study will consist of a minimum of 3 visits for each subject. Each subject will attend a screening visit within 20 days before injection, an imaging visit, and a follow-up visit approximately 2 weeks after injection. During the screening visit, the subjects must satisfy all entry criteria and undergo safety assessments. During the imaging visit, each subject will receive by bolus IV administration, a single dose of ioflupane (¹²³ I) injection with a nominal ¹²³ I activity of 111 MBq ± 10% and will undergo simultaneous whole-body (head to mid-thigh) anterior and posterior planar scintigraphy scans at 10 minutes, 1 hour, 2 hours, 4 hours, 5 hours, 24 hours, and 48 hours after administration. Brain SPECT imaging will be performed at 3 and 6 hours after administration. A reference source will be imaged alongside the subject. Time-activity curves will then be generated from ¹²³ I activity data from all 8 subjects and integrated to obtain the normalised-cumulated activity in each source region, which will then be used along with the Medical Internal Radiation Dosimetry (MIRD) schema to determine the internal radiation dosimetry. The dosimetry will be evaluated for the Cristy-Eckerman female and hermaphrodite male phantoms. For evaluation of the biodistribution and radiation dosimetry, blood (up to 5 mL) samples will be collected at 1 hour before administration of ioflupane (¹²³ I) injection and at the following times after administration: 5, 15, 30 minutes and 1, 2, 3, 4, 5, 24, and 48 hours. Urine excreted from 1 hour before administration of ioflupane (¹²³ I) injection to 48 hours after administration will be collected as voided. At the follow-up visit, all subjects will undergo specified safety assessments, and all female subjects of childbearing potential will also have a urine pregnancy test. All subjects' safety will be monitored during the course of the study. The safety analysis will include the following: 
Adverse events (AEs) up to study exit. | | |

| | | |
|---|---|--|
| Name of Sponsor/Company: GE Healthcare Ltd. and its Affiliates | Individual Study Table Referring to Part of Dossier in Which the Individual Study or Study Table is Presented: | (For National Authority Use Only) |
| Name of Finished Product: DaTSCAN™ | Volume: | |
| Name of Active Ingredient: Ioflupane (¹²³ I) | Reference: | |
| 
 • A tolerability questionnaire to be completed at approximately 1 hour before injection and at approximately 15 minutes, 1, 4, 24, 48 hours after injection. • Physical examination at prespecified time points. • Clinical laboratory tests (serum biochemistry, haematology, and urinalysis) at screening visit (which will be considered baseline), and at approximately 3 hours, 48 hours, and 2 weeks after injection. • Injection site monitoring (at baseline, at approximately 1 hour before injection, and at approximately 4 hours after injection). • Vital signs and oxygen saturation (at screening visit; at baseline; at approximately 1 hour before injection; and at approximately 10, 20, and 30 minutes; approximately 1, 2, 4, 24, and 48 hours; and approximately 2 weeks after injection). • 12-lead electrocardiogram (ECG) (at screening visit, at approximately 1 hour before injection, and at approximately 2 and 5 hours after injection). • Concomitant medications. | | |
| 
Selection of Subjects:
 
Inclusion Criteria:
 
To be included in this study, a subject will have to meet all of the following criteria:
 
 (1) Chinese male or female who has agreed to sign and date the written informed consent form (2) Age 18-70 years (3) Body mass index (BMI) of 18-30 kg/m² (4) General good state of health as judged by a qualified physician after completing physical examination (5) Fit, co-operative, and able to provide consent 
Exclusion Criteria:
 
Subjects are to be excluded from this study if they meet any of the following criteria:
 
 (1) Sensitivity to DaTSCAN™ ioflupane (¹²³I) injection or any of its ingredients (2) A history of motor disturbances (3) A history of pulmonary, cardiovascular, neurological, renal or hepatic, hormonal or coagulation disorders or hyperthyroidism (4) A history of drug, alcohol, or solvent abuse (5) The subject has been previously enrolled in this study or participated in a clinical study involving an investigational pharmaceutical product within 30 days prior to screening (6) Radionuclide injection within a minimum of 5 radioactive half-lives prior to screening (7) Use of any medication (except paracetamol [acetaminophen] or oral contraceptive), including traditional Chinese medicine, within 2 weeks prior to the imaging visit (8) Classification as a radiation worker (9) Women of child-bearing potential not accepting a highly effective method of birth control (A woman is considered of child-bearing potential, i.e., fertile, following menarche and until becoming post-menopausal unless permanently sterile. Permanent sterilisation methods include hysterectomy, bilateral salpingectomy and bilateral oophorectomy. Postmenopausal is defined as 12 months with no menses without an alternative medical cause, in International Council on Harmonisation (ICH) M3 (R2); A highly effective method of birth control is defined as one which results in a low failure rate (i.e., less than 1 % per year) when used consistently and correctly, such as implants, injectables, combined oral contraceptives, some intrauterine devices, sexual abstinence or vasectomised partner, in ICH M3 (R2).) (10) Pregnant or lactating women | | |

| | | |
|--|---|--|
| Name of Sponsor/Company: GE Healthcare Ltd. and its Affiliates | Individual Study Table Referring to Part of Dossier in Which the Individual Study or Study Table is Presented: | (For National Authority Use Only) |
| Name of Finished Product: DaTSCAN™ | Volume: | |
| Name of Active Ingredient: Ioflupane (¹²³ I) | Reference: | |
| Number of Subjects/Centres Planned: A total of 8 adult HVs (4 males and 4 females) at 1 centre | | |
| Treatment of Subjects: 
 Investigational Medicinal Product (IMP): Each subject will receive a single administration of ioflupane (¹²³I) injection by bolus IV injection contralaterally to the sampling catheter. The nominal activity of ¹²³I should be 111 MBq ±10%, in a maximum volume of 5 mL. Standard of Truth: None. Duration of Treatment: The administration of ioflupane (¹²³I) injection will last for 15 to 20 seconds via injection into an arm vein, followed by whole body imaging, brain SPECT imaging, etc. The duration of the imaging visit will last approximately 48 hours after injection of IMP. | | |
| Safety and Biodistribution/Dosimetry Variables: 
Safety Variables:
 
Primary Outcome Measures:
 
Safety variables will include monitoring of the following:
 
 Occurrence of AEs up to study exit Results of a tolerability questionnaire to be completed at prespecified time points Results of physical examinations at prespecified time points Results of clinical laboratory tests at prespecified time points Results of injection site monitoring at prespecified time points Results of vital signs (blood pressure, heart rate, body temperature, respiratory rate) and oxygen saturation at prespecified time points Results of ECG examinations at prespecified time points 
Secondary Outcome Measures: Dosimetry estimates and cumulated activity by source region and by entire body (including whole blood, plasma, and excreted urine) at time points up to 48 hours after administration in HVs.
 
Biodistribution/Dosimetry:
 
Biodistribution data in HVs will consist of ¹²³I activity in organs and tissues of interest at multiple time points, ¹²³I activity in whole blood and plasma at multiple time points, and ¹²³I activity in voided urine. The ¹²³I activity in voided urine will be calculated as the product of the ¹²³I activity measured in each void multiplied by the volume of that void. The absorbed doses of radiation to organs and tissues will be evaluated for the Cristy-Eckerman female and hermaphrodite male phantoms. Descriptive statistics of absorbed doses to the target organs and tissues specified in the MIRD schema will be tabulated.
 
Imaging Variables:
 
Planar whole-body scanning will be performed serially at prespecified time points over a period of approximately 48 hours after administration (n=8 HVs). Brain SPECT imaging will be acquired at 3 and 6 hours after administration (n=8 HVs).
 
Statistical Methods and Planned Analysis:
 
Tabulations of summary statistics, graphical presentations, and statistical analyses will be performed with SAS® software. No confirmatory hypothesis testing is intended to be performed. P-values will be interpreted as a metric of uncertainty. All data will be listed by subject number and time point (if applicable). Confidence intervals, both individual and simultaneous, will be at the 95% confidence level unless otherwise noted. The last pre-administration observation will be used as the baseline value for calculating post-administration changes from baseline. Demographic and other baseline information will be summarised.
 
An overall summary of AEs will be presented, and they will be coded with Medical Dictionary for Regulatory Activities (MedDRA) and summarised by MedDRA system organ class and preferred term. Results of the following evaluations performed before and after DaTSCAN™ administration will be summarised with
 | | |

| | | |
|---|---|--|
| Name of Sponsor/Company: GE Healthcare Ltd. and its Affiliates | Individual Study Table Referring to Part of Dossier in Which the Individual Study or Study Table is Presented: | (For National Authority Use Only) |
| Name of Finished Product: DaTSCAN™ | | |
| Name of Active Ingredient: Ioflupane (¹²³ I) | Volume: Reference: | |
| observed values and changes from baseline: physical examinations, 12-lead ECGs, vital signs (blood pressure, heart rate, respiratory rate, and body temperature) and oxygen saturation, injection site monitoring, and clinical laboratory evaluations (haematology, serum biochemistry, and urinalysis). Concomitant medications will be summarised. In addition, results of the tolerability questionnaire given after DaTSCAN™ administration will be summarised in descriptive statistics and boxplot. Dosimetry estimates (using MIRD methods) and cumulated activity by source region and by entire body (including whole blood, plasma, and excreted urine) at time points up to 48 hours after administration will be summarised. The ED as calculated by using International Commission on Radiological Protection (ICRP) methods will be summarised. In addition, the following measures will be compared between the Chinese subjects from this study and European subjects: the normalised cumulative activity, absorbed doses, and ED. These measures will be compared by using the 2-sample t-test. Striatal binding ratios (SBR) will be analysed to determine the stability of striatal uptake relative to a reference region over the proposed imaging window of 3 to 6 hours after administration. The difference between the SBR at 3 and 6 hours calculated for each subject will be tested by Wilcoxon signed-rank test. | | |
| Sample Size Estimates: No sample size calculations were performed. The sample size has been chosen to fulfil local regulatory requirements. | | |

3 LIST OF ABBREVIATIONS AND DEFINITIONS OF TERMS

| | |
|--------|---|
| AE | Adverse event |
| BMI | Body mass index |
| CRF | Case report form |
| CRO | Contract research organisation |
| DAT | Dopaminergic transporter protein |
| ECG | Electrocardiogram |
| ED | Effective dose |
| EDC | Electronic data capture |
| GCP | Good Clinical Practice |
| β-hCG | Beta-human chorionic gonadotropin |
| HV | Healthy volunteer |
| IB | Investigator Brochure |
| ICH | International Council on Harmonisation |
| ICRP | International Commission on Radiological Protection |
| IEC | Independent Ethics Committee |
| IMP | Investigational medicinal product |
| IRB | Institutional/Independent Review Board |
| IV | Intravenous |
| MedDRA | Medical Dictionary for Regulatory Activities |
| MIRD | Medical internal radiation dose |
| PS | Parkinsonian syndromes |
| ROI | Region of interest |
| SAE | Serious adverse event |
| SBR | Striatal binding ratios |
| SOP | Standard operating procedure |
| SPECT | Single photon emission computed tomography |
| TEAE | Treatment-emergent adverse event |
| VAS | Visual analogue scales |
| WBC | White blood cell |

4 BACKGROUND INFORMATION

DaTSCAN™ ioflupane (^{123}I) injection—marketed as DaTscan™ (Ioflupane I 123 injection) in the United States—is a radiopharmaceutical for diagnostic use only. The active substance in DaTSCAN™ is ioflupane (^{123}I), which binds with high affinity to the presynaptic dopaminergic transporter protein (DAT, also known as the dopamine reuptake site).

DaTSCAN™ is approved in Europe, the United States, Hong Kong and Canada for detecting loss of functional dopaminergic neuron terminals in the striatum of patients with clinically uncertain Parkinsonian syndromes (PS), including Parkinson's disease, multiple system atrophy, and progressive supranuclear palsy. DaTSCAN™ is useful for differentiating PS from essential tremor.

In Europe, Singapore, Japan, and Mexico, DaTSCAN™ is also approved for use in adult patients to help differentiate probable dementia with Lewy bodies from Alzheimer's disease. DaTSCAN™ is unable to discriminate between dementia with Lewy bodies and Parkinson's disease dementia.

The current phase 1 study is intended to determine the safety, biodistribution, internal radiation dosimetry, and effective dose (ED) of DaTSCAN™ ioflupane (^{123}I) injection after intravenous (IV) administration in Chinese healthy volunteers (HVs). The results of this study will be compared with corresponding findings from the study of European HVs. The results of this study will be incorporated into a submission to regulatory authorities in the People's Republic of China.

5 STUDY OBJECTIVES AND PURPOSE

The primary and secondary objectives of the study are as follows:

Primary Objective

- To evaluate the safety of a single dose of ioflupane (¹²³I) injection in Chinese HVs.

Secondary Objectives

- To determine the biodistribution, internal radiation dosimetry, and ED of ioflupane (¹²³I) injection after IV administration in Chinese HVs.
- To compare biodistribution and dosimetry findings in this Chinese group with those previously established in European HVs.
- To compare brain single photon emission computed tomography (SPECT) imaging results in this Chinese group with those previously established in European HVs.

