6.2 Study Rationale

The quantity of ioflupane in the 5 mL formulation of DaTSCAN™ ioflupane (^{123}I) injection is 0.625 μg . The pharmacokinetics of DaTSCAN™ ioflupane (^{123}I) injection has been studied in healthy adults. Because administration is IV, absorption is complete and ioflupane (^{123}I) is completely bioavailable.

The pharmacokinetics of DaTSCAN™ ioflupane (^{123}I) injection were studied by monitoring radioactivity after IV injection. Similar studies have already been done to evaluate the pharmacokinetics of DaTSCAN™ ioflupane (^{123}I) injection in European subjects [Study CY 95.FP.1], [Frear 1998] and Japanese subjects (Study NMA98P1 [Takano et al 1999]). The current study will involve Chinese subjects.

In this study, anterior and posterior whole-body images will be obtained by using a 2-headed gamma camera at 10 minutes, 1 hour, 2 hours, 4 hours, 5 hours, 24 hours, and 48 hours after injection of DaTSCAN™. A dual-head scintillation camera, medium-energy collimator, and standard imaging techniques will be used. An external ^{123}I calibration source will be imaged alongside the subject.

Biodistribution of ^{123}I after administration of DaTSCAN™ will be measured by whole-body imaging in conjunction with serial blood and urine sampling. From regions of interest (ROIs) placed upon conjugate anterior and posterior whole-body images, the activities in the brain, striatum, thyroid, lungs, liver, spleen, stomach, heart, and intestines will be determined. The data will be used to calculate initial organ uptake, normalised cumulative activity, absorbed organ dose and the ED, according to the methodology of MIRD [Siegal et al 1999] and the International Commission on Radiological Protection (ICRP) [ICRP 1991].

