10.2.2 Assessment of Striatal Binding Ratio

Left and right striatal binding ratios (SBR) will be determined from brain SPECT images acquired at 3 and 6 hours after administration.

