12.6 Secondary Analysis

12.6.1 Biodistribution

By using activity data from ROIs, data from the whole-body images, as well as activity data from serial blood and urine samples, descriptive statistics will be generated for biodistribution data (decay-corrected percentage administered activity per organ) at each time point for each organ and tissue of interest in HVs. Time-activity curves will then be generated from ^{123}I activity data from all 8 subjects and integrated to obtain the normalised-cumulated activity in each source region, which will be summarised with descriptive statistics. The amount of ^{123}I activity in plasma and excreted in urine will be calculated from the product of concentration of ^{123}I activity measured in each sample and the volume of each sample.

The cumulative amount of ^{123}I activity excreted in urine will be tabulated for each subject and summarised. In addition, the normalised cumulative activity in each source region will be compared between the Chinese subjects from this study and European subjects by using the 2-sample t-test.

SBR will be analysed to determine the stability of striatal uptake relative to a reference region over the proposed imaging window of 3 to 6 hours after administration. The difference

between the SBR at 3 and 6 hours calculated for each subject will be tested by Wilcoxon signed-rank test.

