12.6.2 Radiation Dosimetry

Descriptive statistics of absorbed doses to the target organs and tissues specified in the MIRD schema will be tabulated. In addition, the absorbed doses to these target organs and tissues will be compared between the Chinese subjects from this study and European subjects by using the 2-sample t-test.

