12.6.3 Effective Dose

ED will be calculated according to ICRP methodology of ICRP publication 60 [[ICRP 1991](#)]. In addition, the ED will be compared between the Chinese subjects from this study and European subjects by using the 2-sample t-test.

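### The secondary objective of comparing brain SPECT results with European healthy volunteers has no matching analysis; SBR is tested only within subject, 3 h against 6 h

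*Combined protocol and SAP*

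**What the plan says.** The third secondary objective, in Section 5 and repeated in the synopsis, is "To compare brain single photon emission computed tomography (SPECT) imaging results in this Chinese group with those previously established in European HVs". It is listed separately from the objective of comparing biodistribution and dosimetry with European volunteers.

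The SPECT measure is defined in Section 10.2.2: "Left and right striatal binding ratios (SBR) will be determined from brain SPECT images acquired at 3 and 6 hours after administration". Section 12.6.1 states why it is analysed: "SBR will be analysed to determine the stability of striatal uptake relative to a reference region over the proposed imaging window". The same section gives the method, in which the difference "between the SBR at 3 and 6 hours calculated for each subject will be tested by Wilcoxon signed-rank test". The synopsis plans the same analysis.

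On European comparisons, the synopsis says "the following measures will be compared between the Chinese subjects from this study and European subjects: the normalised cumulative activity, absorbed doses, and ED". The body follows that list. Section 12.6.1 applies a two-sample t-test to normalised cumulative activity. In Section 12.6.2 "the absorbed doses to these target organs and tissues will be compared between the Chinese subjects from this study and European subjects", and in Section 12.6.3 "the ED will be compared between the Chinese subjects from this study and European subjects by using the 2-sample t-test". SBR appears in none of these.

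Section 4 says in general terms that the results will be set against those of the European study. It names no SPECT variable, time point or method.

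**The concern.** An objective needs an estimate or a test that can answer it. Here the only SBR analysis compares each Chinese subject with himself or herself at two times. It can show whether SBR is stable between 3 and 6 hours, but it says nothing about whether SBR in Chinese volunteers resembles SBR in European volunteers.

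Two things are at stake. First, if the plan is followed exactly, the report has no result for one of its stated secondary objectives, in a study whose results are meant for a submission to the Chinese authorities (Section 4). Second, if the gap is filled at reporting, the choices are open after the data are seen. There are two time points and three ways to express SBR (left, right or their mean), so 2 × 3 = 6 versions of the comparison, before any choice of European data source. The study is open-label, and a comparison added late would also have to be reported under Section 12.12 as a deviation from the planned analysis.

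**Working it through.** **Step 1: match each objective to an analysis.**

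| Objective (synopsis, Section 5) | Planned analysis |
|---|---|
| Safety of a single dose | Section 12.5, descriptive summaries |
| Biodistribution, dosimetry and effective dose in Chinese volunteers | Sections 12.6.1 to 12.6.3, descriptive statistics |
| Biodistribution and dosimetry versus European volunteers | Sections 12.6.1 to 12.6.3, two-sample t-tests on three measures |
| Brain SPECT results versus European volunteers | None |

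**Step 2: check whether another analysis covers the last row.**

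- The t-test on normalised cumulative activity is applied to each source region, and the striatum could be one of them. But Section 6.2 takes these activities from regions "placed upon conjugate anterior and posterior whole-body images, the activities in the brain, striatum" and other organs. That is planar whole-body data, not SPECT.
- Section 10.2.4 describes region-of-interest counts from images in general, and Section 12.6.7 tabulates uninterpretable images. Neither contains a European comparison.
- Section 12.1 sets general descriptive statistics. Applied to SBR, they would summarise the Chinese group only.
- The Imaging Manual is cited for imaging, blood and urine procedures. Nothing in the protocol says that it holds a between-group analysis.
- The European study CY 95.FP.1 is cited in Sections 6.2, 8.3 and 14. The documents do not say whether it holds SPECT or SBR data, or how many subjects it had.

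**Step 3: precision if an SBR comparison is added.** The plan makes no sample size or power calculation (Sections 12.8 and 12.9), so there is no figure to reproduce. This step is illustrative.

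Inputs: 8 Chinese subjects (Section 6.1); 95% confidence level (Section 12.5); European number nE, not given and therefore assumed; common SD in both groups, also assumed.

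Half-width in SD units = t(0.975, 8 + nE − 2) × √(1/8 + 1/nE)

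| Assumed nE | t | √(1/8 + 1/nE) | Half-width (SD) |
|---|---|---|---|
| 6 | 2.179 | 0.540 | 1.18 |
| 8 | 2.145 | 0.500 | 1.07 |
| 12 | 2.101 | 0.456 | 0.96 |
| 20 | 2.056 | 0.418 | 0.86 |
| very large | 1.960 | 1/√8 = 0.354 | 0.69 |

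The last row depends on the common-SD assumption. Without it, and with a very large European group, the half-width tends to t(0.975, 7)/√8 = 2.365/2.828 = 0.84 SD of the Chinese group.

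By noncentral-t calculation, the true difference detectable with 80% power at the two-sided 5% level is 1.65 SD at nE = 6 and 1.22 SD at nE = 20. No SBR standard deviation is given, so none of these figures can be put into SBR units.

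**The case against.** The strongest reply is that comparing with previously established results need not mean a formal two-group analysis. The study is described as noncomparative, with no confirmatory testing (Section 12.6.4) and no power calculation. Section 4 commits to setting the results against the European study, and Section 12.1 provides general descriptive statistics, so a side-by-side description in the report would be compatible with the plan. The log for Amendment A01 (Section 16.1.2) adds that the 3 and 6 hour SPECT results were introduced to support label wording on the imaging window, which is the question the paired test answers. The objective may simply be worded more broadly than intended.

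Part of this stands. A formal test is not needed, and rewording is a legitimate remedy. But under the same noncomparative design, the plan names a method for each of the other European comparisons and leaves SPECT out of the synopsis list. A descriptive comparison would still need a European source, a time point and a side, and none is given. The amendment log explains one use of the scans but does not alter the current objective.

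It is also fair to object that the half-widths measure the remedy, not the defect, and that they cover sampling error only. Differences in camera, reconstruction or region definition between the two studies would add to them. The finding rests on the match between objectives and analyses, not on these figures.

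**Conclusion.** The concern holds. One of the stated secondary objectives has no analysis: three measures are named for European comparison, and none comes from SPECT. This conclusion rests on the text alone and needs no assumption.

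The consequence is limited to that objective, and correction before SBR data are reviewed is worthwhile and proportionate. The precision of any added comparison is low: about 1.18 to 0.86 SD half-width for an assumed 6 to 20 European subjects. Even an unlimited European group would leave about 0.69 SD under a common SD, or 0.84 SD without that assumption. This supports reporting an estimate with its interval and not relying on a significance test.

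**What to change.** First establish whether comparable European SBR data exist, in CY 95.FP.1 or elsewhere. Then, before SBR data are reviewed, do one of the following.

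1. **Data exist.** In the synopsis and Section 12.6.1, add the Chinese minus European mean SBR difference with a 95% confidence interval. Name the European source, the time point or points (3 h, 6 h or both) and whether left, right or mean SBR is used. Present it as an estimate, and state differences in image acquisition or processing as a limitation.
2. **Data do not exist.** Remove the objective from the synopsis and Section 5, or reword it to the 3 h versus 6 h stability question that is already analysed.

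Naming SBR in the secondary outcome summary (synopsis and Section 10.2) would be tidying only.

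Neither option needs new scans or visits. Option 1 requires retrieval of European SBR data (mean, SD and number of subjects are enough for the interval) and yields an imprecise estimate. Option 2 gives up the between-population SPECT comparison. Section 13.1 requires prior ethics committee approval of a written amendment, with limited exceptions. The sponsor should also consider whether removing the objective is consistent with the regulator's ICH E5 request recorded for Amendment A01 (Section 16.1.1).
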